13.0 Risks to Participants

Foreseeable Risks: The study has the following risks:

- infection (< 1%)
- bleeding (< 1%)
- nerve injury (< 1%)
- cardiac arrhythmias (irregular heartbeat) (< 1%)
- respiratory complications (< 1 %)

PROTOCOL TITLE: Prospective Randomized controlled trial comparing liposomal bupivacaine to bupivacaine Interscalene blocks for total shoulder arthroplasty surgery

VERSION DATE: 7/6/2020

These complications all fall within the standard risks of surgery and the performance of the interscalene injection. Any intervention being provided as a part of this study falls within the standard of care as both medication options are within the standard treatments for post-operative pain and are currently used as analgesic options at UMMC.

EXPAREL contains bupivacaine. Serious side effects related to bupivacaine are not common, but may occur if too much is given or if it is accidentally injected into a blood vessel. When given incorrectly, side effects may involve the brain or the heart.

The effects on the brain and central nervous system may include:

- Restlessness (< 2%)
- Anxiety (<2%)
- Dizziness (<2%)
- Tinnitus (ringing in the ears) (<2%)
- Blurred vision (<2%)
- Tremors (shaking) possibly proceeding to convulsions (<2%).

The effects on the heart appear when too much bupivacaine is given or when bupivacaine is injected in a blood vessel by accident. These effects cause a decrease of the heart function, including low heart rate or abnormal heart rhythm, decreased blood flow, low blood pressure, and, in extreme cases, heart attack. (<2%)

The numbing sensation caused by bupivacaine may be persistent, with slow, incomplete, or no recovery. Sometimes a tingling sensation may appear in the area treated with bupivacaine. When injected next to a large nerve, bupivacaine may cause weakness or paralysis.

Allergic reactions are rare, but may include rash, itching and redness of the skin, sneezing, nausea, vomiting, dizziness, fainting, sweating, fever, and low blood pressure.

Other side effects of liposomal bupivacaine when given into the wound include:

- Nausea (22.6%)
- Constipation (8.7%)
- Vomiting (6%)
- High temperature (5.5%)
- Dizziness (<2%)
- Swelling (<1%)
- Low blood pressure (<2%)

PROTOCOL TITLE: Prospective Randomized controlled trial comparing liposomal bupivacaine to bupivacaine Interscalene blocks for total shoulder arthroplasty surgery

VERSION DATE: 7/6/2020

- Anemia (<1%)
- Itching (2.4%)
- High heart rate (1.3%)
- Headache (5%)

Reproduction Risks:

If the patient were pregnant we would not perform the study on them. If they were to become pregnant there are no known risks to the patient.

Risks to Others: N/A

14.0 Potential Benefits to Participants

Potential Benefits: The potential benefits of participating in this study include reduced pain following shoulder surgery and shortened hospital stay.

15.0 Statistical Considerations

Data Analysis Plan: We plan to collect our data using excel, which will be maintained in box. When the study is completed and ready for statistical analysis the data will be shared with our staff statistician.

Power Analysis: Following the pilot study of 30 patients, it was determined that 40 additional patients (for a total of 70 patients, 35 per group) would need to be enrolled to reach 80% power.

Statistical Analysis: This study will be analyzed by our staff biostatistician. The data will be deidentified and shared with him in box. The statistician will be provided the protocol so they are able to analyze for primary and secondary objectives.

Data Integrity: All patients will be assigned a unique patient identifier. The data that will be sent to the statistician will be deidentified.

16.0 Confidentiality

Data Security: All paper documents and consent forms will be stored in a locked cabinet in the anesthesia research office in B573 Mayo. All study data will be stored electronically in Box and only the PI and members of the research team will have access to the data.

17.0 Provisions to Monitor the Data to Ensure the Safety of Participants

PROTOCOL TITLE: Prospective Randomized controlled trial comparing liposomal bupivacaine to bupivacaine Interscalene blocks for total shoulder arthroplasty surgery

VERSION DATE: 7/6/2020

Data Integrity Monitoring.

The PI, co-investigators, and research assistants will all have access to the study data stored in the University's Box storage system. All the research assistants have experience collecting pain scores and other relevant study information. The PI of the study will periodically review the study data to ensure accuracy and completeness of study data.

Data Safety Monitoring: The Department of Anesthesiology has established a Data and Safety Monitoring Committee consisting of several staff anesthesiologists which include persons who are board certified as pain specialists. Data will be transmitted in box to persons on the board on a monthly basis for review. If there are patterns of adverse events, the board will meet as needed and provide recommendations.

All safety data will be collected on a case report form and transferred into an excel spread sheet that will be stored in box. Also, all phone call data will be collected on a case report form and transferred into excel in box.

All data will be collected by research assistants on a daily basis. Subjects are monitored at several intervals on day of surgery and daily up to 72 hours. If the patient is discharged prior to 72 hours they will Who will review the data.

The data will be reviewed on a regular basis (weekly) by the PI and research staff. If there are consistent complications noted a meeting will be convened by the DSMB for recommendations.

The statistical tests for analyzing the safety data to determine whether harm is occurring.

The statistician uses R or SAS for analysis. Most likely a regression analysis will be performed to see which event is most likely the contributor for the complications. Also a chi-square analysis can be performed. All is very dependent on data variability.

A fatal or serious adverse event that is attributable to either the delivery or the study medication itself.

18.0 Provisions to Protect the Privacy Interests of Participants

Protecting Privacy:

PROTOCOL TITLE: Prospective Randomized controlled trial comparing liposomal bupivacaine to bupivacaine Interscalene blocks for total shoulder arthroplasty surgery

VERSION DATE: 7/6/2020

Patients will be asked if this is a good time to answer questions. All patients will have the right to refuse to answer questions when called. All calls will be done in a secure office and the data is deidentified when entered. It will be stored using a unique study identifier.

Access to Participants:

All patients are required to sign a consent that states their privacy of the data being collected. In addition, they are required to sign a HIPAA consent that further describes the data being collected. It also describes that all data is deidentified and stored in a secure database. They will be informed that data is stored and reviewed in a box which is HIPAA compliant and that only study personnel have accesss.

19.0 Compensation for Research-Related Injury

Compensation for Research-Related Injury:

In the event that this research activity results in an injury, treatment will be available, including first aid, emergency treatment and follow-up care as needed. Care for such injuries will be billed in the ordinary manner, to the patient and/or insurance company.

Contract Language: N/A

20.0 Consent Process

Consent Process (when consent will be obtained): Patients will be identified in the pre-operative time period by the surgeons and if possible will be consented by the research coordinator or research assistant. If patients have more questions and do not want to sign at their clinic will be asked if it is allowable for a study staff member to contact them prior to surgery via phone to clarify if they have any questions. On the day of surgery, if the patient has not already signed consent and is still interested in participating in the study they will be presented with consent and Health and Insurance Portability and Accountability Act (HIPAA) forms. The patient will review the forms with the surgeon, research staff, or anesthesiologist, with the REDCap e-consent process being preferentially used. Subjects will be reminded that participation is completely voluntary, and that they may stop participation at any time without question or penalty. The surgeon, research staff, or anesthesiologist will answer any questions that the subjects may have about the study. If the patient decides to participate, they will be asked to sign the consent and HIPAA forms. One copy will be saved for study records, and the subject will be provided with a copy of the forms for their own records.

PROTOCOL TITLE: Prospective Randomized controlled trial comparing liposomal bupivacaine to bupivacaine Interscalene blocks for total shoulder arthroplasty surgery

VERSION DATE: 7/6/2020

Waiver or Alteration of Consent Process: N/A

Non-English Speaking Participants: N/A- No Non-English speaking patients will be enrolled in this study.

Participants Who Are Not Yet Adults: N/A

Cognitively Impaired Adults, or adults with fluctuating or diminished capacity to consent: N/A

Adults Unable to Consent: N/A

21.0 Setting

Research Sites: Patients will be consented in the surgeon's clinic, pre assessment clinic, or preoperative area. The surgical procedures will take place at the M health Ambulatory Surgery Center or Fairview Riverside campus.

International Research: N/A

22.0 Multi-Site Research N/A

23.0 Resources Available

Resources Available:

Research assistants are available to aid in consent and data acquisition. All research assistants will be familiar with the study protocol and have experience working with similar studies.

We plan to enroll 70 subjects. The plan is to screen 90 subjects to research this target population. This center performs approximately 300 TSAs annually. We plan to conduct this study over 3 months. Enrollment and data collection will be completed at this time. Statistical Analysis will take approximately two months to complete.

All procedures will be performed in the clinical facilities at the MHealth Clinics and Surgery Center and at the west and East Bank. Data storage and analysis will be done using desktop equipment which is available at the Research Office B573 Mayo.

In the event that this research activity results in an injury, treatment will be available, including first aid, emergency treatment and follow-up care as needed.

PROTOCOL TITLE: Prospective Randomized controlled trial comparing liposomal bupivacaine to bupivacaine Interscalene blocks for total shoulder arthroplasty surgery

VERSION DATE: 7 6/3/2020

Care for such injuries will be billed in the ordinary manner, to the patient and/or insurance company.

All study personnel will be adequately trained by the Principle Investigator on the study protocol and study conduct. A log will be maintained to track which personnel are trained. A delegation of authority log will also be maintained to track which personnel are responsible for specific duties.

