23.0	Resources Available.....	18
24.0	References.....	19

PROTOCOL TITLE: Prospective Randomized controlled trial comparing liposomal bupivacaine to bupivacaine Interscalene blocks for total shoulder arthroplasty surgery

VERSION DATE: 7/6/2020

ABBREVIATIONS/DEFINITIONS

- LB/ liposomal bupivacaine
- TSA/total shoulder arthroplasty
- QOR/Quality of Recovery
- RCR/rotator cuff repair
-

PROTOCOL TITLE: Prospective Randomized controlled trial comparing liposomal bupivacaine to bupivacaine Interscalene blocks for total shoulder arthroplasty surgery

VERSION DATE: 7/6/2020

STUDY SUMMARY

Study Title	Prospective Evaluation of Liposomal bupivacaine in Total Shoulder Surgery
Study Design	Prospective randomized double blind
Primary Objective	Total opioids in 72 hours
Secondary Objective(s)	Pain scores within 72 hours, QOR at 72 hours and 14 days, Number of phone calls to surgeon, adverse events, time to discharge
Research Intervention(s)/Investigational Agents	Liposomal bupivacaine and bupivacaine vs bupivacaine
Scientific Assessment	HRPP facilitated scientific assessment
IND/IDE # (if applicable)	Study Medication has been approved for use in shoulder surgery April 6, 2018
IND/IDE Holder	Pacira Pharmaceuticals
Investigational Drug Services # (if applicable)	N/A
Study Population	Adult patients aged 18 and older who are undergoing total shoulder arthroplasty
Local Sample Size (number of participants recruited locally)	90

PROTOCOL TITLE: Prospective Randomized controlled trial comparing liposomal bupivacaine to bupivacaine Interscalene blocks for total shoulder arthroplasty surgery

VERSION DATE: 7/6/2020

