While in the hospital all patients will receive a standardized multimodal pain medication regimen. Acetaminophen 975 mg q6 hours, ibuprofen 600mg q6 hours and prn oxycodone 5-10 mg q4 hours or 2-4 mg hydromorphone oral every 4 hours. All patients will be discharged with 30-40 pills of 5 mg oxycodone or 30-40 pills of hydromorphone 2 mg with instructions to take 5-10 mg oxycodone for severe pain every 4 hours as needed or 2-4 mg every 4 hours hydromorphone as needed for severe pain. Patients will be instructed to start with the lower dose, but can repeat the dose if needed up to 10mg oxycodone or 4mg hydromorphone every 4 hours if needed.

Assessments: Post-operatively patients will be evaluated at 2 and 6 hours post-operatively by a blinded research staff. This person will not be aware of the patient's mode of analgesia. The patients will be contacted via in person assessment or via telephone at 24, 48, and 72 hours +/- 5 hours. Patients will be asked to rate their pain on scale of 0-10. The amount of opioids used by the patient will be recorded by study personnel as will any other adjuvant pain medication used. The time in phase 1 and phase 2 of PACU will be recorded. The patients will be asked at 72 hours post-injection if they would undergo an interscalene block with their medication again or if they would choose a different form of pain management (ex: higher doses of pain medications). Patients will fill out a Quality of Recovery Survey at 72 hours and 14 days, and be assessed for block related complications at this time. As part of the research, patients also will undergo diagnostic ultrasound of their diaphragm on POD 1. All complications will be recorded including:

- Failure of the block
- Wound infections
- Subsequent procedures
- Complications related to placement of the interscalene block including nerve injury, prolonged sensory loss greater than three days, prolonged arm weakness greater than three days
- Opioid related side effects of nausea and/or vomiting
- Local anesthetic toxicity as evidenced by seizures or cardiovascular collapse without other reasonable etiology

All data will be recorded on the Clinical Diagnostic Sheet and will then be given to the research coordinator for manual data entry. Data collection will continue until POD #14. At that time study participation will be terminated. Should patients be re-admitted to the hospital in the next two weeks (Up to POD 30) for pain, a notation will be made in study records.

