8.0 Study Population

Inclusion Criteria: All adult patients aged greater than 18 years of age that are undergoing total or reverse total shoulder arthroplasty

Exclusion Criteria: Patients with allergy to local anesthetics, daily use of opioids for more than 3 weeks prior to surgery, patient refusal and those who have opted out of research, patients with coagulopathy, non-english speaking patients, and those who do not have access to a telephone.

Screening: Patients will be screened at their preoperative visit either in the surgeon's office, pre assessment center, or preoperative area.

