10.0 Local Number of Participants

Local Number of Participants to be consented: 90 patients as we expect a drop out or loss to follow up of 20%.

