12.0 Withdrawal of Participants

Withdrawal Circumstances: Subjects who have consented prior to the day of surgery and for some reason choose not to participate will be withdrawn and a notation will be made in the study records and these people will be considered screen failures. The surgeon may choose to withdraw the patient from the study prior to surgery for any medical reason or if they suffer a major life threatening adverse event.

Withdrawal Procedures: If the patient is withdrawn from study prior to the procedure, they will be noted in study records as screen failures. If they undergo the procedure and they decide they no longer want to be a part of the study or withdrawn by the physician, they will be withdrawn and no further data will be collected. This will also be noted in the study documentation.

Termination Procedures: If the study is terminated for any reason, or there is more than 5 % major adverse events the data that is already collected will be stored in a secure location only accessible to research personnel on this study. No further data will be collected if the study is terminated.

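### Section 23 (screen 90, enrol 70) conflicts with section 10 (consent 90 to absorb 20% loss); followed literally, it leaves no margin for loss around the 70 that section 15 ties to 80% power

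*Combined protocol and SAP*

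**What the plan says.** Four places in the combined protocol and SAP give the numbers.

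- **Study summary:** the row "Local Sample Size (number of participants recruited locally") has the value 90.
- **Section 10.0:** the number to be consented is "90 patients as we expect a drop out or loss to follow up of 20" per cent.
- **Section 15.0, Power Analysis:** after a pilot of 30, "40 additional patients (for a total of 70 patients, 35 per group) would need to be enrolled to reach 80% power".
- **Section 23.0:** "We plan to enroll 70 subjects. The plan is to screen 90 subjects to research this target population".

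Other places bear on what the terms mean. Section 12.0 says of early withdrawals: "If the patient is withdrawn from study prior to the procedure, they will be noted in study records as screen failures". Of patients who leave after the procedure it says "they will be withdrawn and no further data will be collected". Section 8.0 uses the word differently: "Patients will be screened at their preoperative visit either in the surgeon's office, pre assessment center, or preoperative area". The primary outcome in section 3.0 is opioid use over 72 hours, while under section 5.0 "Data collection will continue until POD #14".

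**The concern.** Section 10 treats 90 as the number who come in and roughly 70 as the number left after losses. Section 23 treats 70 as the number who come in, and uses 90 for the pool they are drawn from. A surplus at screening does not protect against loss after enrolment.

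Such loss is foreseeable. Section 10 names loss to follow-up as part of its 20%. Section 12 provides for withdrawal after the procedure. For patients who have been discharged, section 5 gathers the opioid data by telephone and diary.

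At stake is the power of the primary comparison. A team working from section 10 would go on until 90 had consented, and a team working from section 23 would aim for 70 enrolled. The plan does not say which count ends recruitment.

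**Working it through.** **Inputs from the documents:** 90 (summary, sections 10 and 23); 20% loss (section 10); 70 in total, 35 per group, 80% power, made up of 30 pilot and 40 further patients (section 15); 70 enrolled (section 23).

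**1. Reproduce section 10's figure.** Number needed = target / (1 − loss) = 70 / 0.80 = 87.5, rounded up to 88. The stated 90 covers this. Forward check: 90 × 0.80 = 72, which is above 70. The allowance in section 10 is therefore adequate.

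**2. Apply section 23 literally.** The fall from 90 to 70 is (90 − 70)/90 = 22.2%. That is already more than the 20% allowance, and it is used up by the time of enrolment. With 70 enrolled, the margin for later loss is 70 − 70 = 0.

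**3. What would have to be enrolled to keep 70 evaluable.** If the whole 20% fell after enrolment and before 72 hours, 88 would be needed. If the 30 pilot patients are complete and only the further 40 are exposed to loss, the figure is 30 + 40/0.80 = 80. Both exceed 70.

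**4. Which losses count.** Only loss before the 72-hour opioid data are complete affects the primary outcome. Loss between 72 hours and day 14 does not. The plan does not divide its 20% between before and after enrolment, or between before and after 72 hours.

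**5. Power illustration, on assumed inputs.** Section 15 states no test, alpha, effect or SD, so its 70 cannot be re-derived. I assume a two-sided 5% two-sample t-test with equal groups and solve for the effect that gives exactly 80% at 35 per group: 0.679 SD. Holding that effect fixed:

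| Evaluable total | How it arises | Power |
|---|---|---|
| 72 | 90 × 0.80 (section 10) | 81.1% |
| 70 | no loss | 80.0% |
| 68 | 30 + 40 × 0.95 | 78.8% |
| 66 | 30 + 40 × 0.90 | 77.6% |
| 62 | 30 + 40 × 0.80 | 74.9% |

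Losing 5% to 20% of the 40 further patients thus gives about 79% to 75%.

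**6. Pilot patients.** If the 30 are within the 90, then 90 − 30 = 60 further patients are to be consented; if not, 90 are. Section 15 counts the pilot within the 70, and 90 is close to 70 inflated for 20% loss, so the natural reading is that they are within. The plan does not say so.

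**The case against.** The strongest defence is that sections 15 and 23 use *enrol* loosely for patients who complete. Read with section 10, 90 would then enter and about 70 would finish, so only the wording is at fault and no power is lost. A second defence uses section 12: consented patients withdrawn before the procedure are screen failures, so screening 90 may simply mean consenting 90.

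The first reading may well be what the sponsor intends, but the text does not say it. Enrolled does not ordinarily mean completed, and section 23 sets enrolment against screening, not against completion. The second reading leaves the problem in place: the 20 patients between 90 and 70 would be gone before the procedure, with no cover for loss after it. Section 8 also uses screening for review at the preoperative visit, so the term is not settled.

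Parts of the defence stand, and they rule out stronger readings that a reader might infer:

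- **That the plan has no allowance for loss.** It has one, in section 10, and it is large enough. The fault is the conflict between sections.
- **That section 23 stops enrolment at 70.** It states a plan to enrol 70; no stopping rule is written.
- **That 90 has three conflicting meanings.** Recruited and consented are compatible. Only the screening label departs.
- **That power falls to about 70%.** That needs 20% of all 70 lost before 72 hours (70 × 0.80 = 56 evaluable; 70.4% on the assumptions above). It counts the 30 pilot patients as exposed to loss, although section 15 says the pilot preceded the power calculation, and it puts every loss before 72 hours. The documents support neither step.

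**Conclusion.** The point holds as an inconsistency in a sample size on which the trial relies. Section 23 cannot be followed together with section 10 as both are worded. Under section 10 the trial expects about 72 evaluable patients and meets its target. Under a literal section 23, any loss before 72 hours leaves fewer than the 70 that section 15 requires for 80% power.

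The conflict and the counts rest on the documents' own figures. The size of the power loss does not: it depends on the assumed test and alpha, on the back-solved effect, and on loss confined to the 40 further patients. On that footing the shortfall is about 1 to 5 percentage points. This should be corrected, but it does not show that the trial is seriously underpowered.

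**What to change.** In section 23, replace the enrol and screen sentences with:

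> *We plan to consent 90 patients in total, and recruitment ends at 90 consented; with 20% loss this leaves about 72 with evaluable 72-hour opioid data, against the 70 (about 35 per group) needed for 80% power.*

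The word *about* is needed because section 5 describes a random number generator consulted just before the block and mentions no blocking, so equal groups are not assured.

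In section 15, call 70 the evaluable number and state whether the 30 pilot patients count within the 90. Keep screened, consented, enrolled and evaluable as separate counts, and use them in the same sense in the summary and section 10.

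If 90 consented is what is meant, the cost is wording only, since 90 is already the stated local sample size. If 70 enrolled is the real ceiling, the sponsor should instead restate the power from its own pilot inputs at the number expected to be evaluable.
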